### Recruitment

In order to generate sufficient data for the development of this research a sample size of (n= 66) patients will be recruited based on previous and concluded RCT for the treatment of LBP or PP (41–43). It was calculated that a sample size of 33 women per cohort could detect a difference in outcomes of 1.0 between the VR intervention and control groups, given a SD of 1.5 and a power of 0.80.

The strategies to achieve an adequate inclusion of participants that reach the target sample size include the multidisciplinary collaboration of the gynecology, rehabilitation and physiotherapy department. The collaborators have been informed about the characteristics of the study in personal interviews and presentation. Recruitment of patients must have a socio-demographic diversity in relation to their social origin, gender, ethnicity and education adapted to the particularities of the reference population.

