#### Data collection, monitoring, and management

Once participants have been informed and agree to participate in the study, data will be collected for statistical analysis. This data collection will take place in the period September-December 2022. Initial assessment (Pre) and final 4-week assessment (Post) will be carried out by the research team including, rehabilitation and physiotherapy department. The data will be aggregated to research database created for this purpose and managed by the principal's researches using exportable data tables for statistical analysis.

The research is designed in 4 stages as presented at Figure 1 study design flow diagram:

Stage 1 includes 2 different processes: firstly the identification of candidates, the provision of prior information and the signing of informed consent if subjects agree to participate. Secondly, the assessments by the physiotherapy department. The initial assessment includes a self-made clinical interview for anamnesis with self-administered questionnaires, which will be completed including FACS, RMDQ, ODI and VAS (T0-Pre). This stage ends with the referral to the physiotherapy intervention team.

Stage 2 includes: Design of a personalised physiotherapy programme (CG and EG) according with Physiotherapy department plus VRi intervention in the (EG).

Stage 3 includes: 4 weeks physiotherapy intervention plus VRi program with the supervision of the physiotherapy department. Initials 1 to 1 session is offered with technology management and patient education. Daily follow up sessions include the progression and adverse events records. Physiotherapy team will update programmes according to participant's feedback.

Stage 4 includes: Final assessments and evaluation (T1-Post). At this stage Physiotherapy team and principals researches compile the results of outcomes after 4 weeks including FACS, RMDQ, ODI, VAS and USEQ. Satisfaction questionnaire will be added to research data's for statistical analysis.

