#### [Statistical analysis](#)

This research is a multicentre prospective controlled trial pre/post design. The results of the trial research will be presented as a summary of the outcome measures, together with the estimated effect size and precision. Statistical analysis will be performed according to the intention-to-treat principle. Patient characteristics will be summarized using frequencies and percentages for categorical factors, and using means and standard deviations for continuous measures in order to have as much information as possible available for exploration and analysis. The effect sizes will be calculated using the Cohen's d so that the results can be compared to other studies. The outcome measures will be compared before and after the completion of the 4 weeks program. All statistical analyses will be conducted using SPSS software. Statistical significance was set at  $p < 0.05$ .

[figure not shown]

Figure 1. Study design flow diagram: Enrollment, assessments and intervention stages

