#### Discussion:

Evidence from single studies suggests that some therapy modalities or a multi-modal intervention (manual therapy, exercise and education) improves pelvic pain and pregnancy related outcomes. However, the current scientific evidence leaves many issues unresolved like type and intensity of exercise and physiotherapy intervention effectiveness for different outcomes. Since evidence showing that one form of exercise is better than another is not available, guidelines recommend exercise programmes that take individual needs, preferences, and capabilities into account in deciding about the type of exercise. This lack of standardized exercise programmes may lead to significant intervention biases in the different studies and consequently the low or moderate level of evidence.

Due to the high prevalence, the recurrence, the interference on daily activities, work capacity and sick leaves, and the increased psychological stress (1–4), low back pain is undoubtedly the key clinical sign to address in this population.

The VRi used in this case may alleviate pain by distracting the patient's attention from pain. The alleviation of pain is thought to be the psychological effect of immersion in the virtual space created by the VR technology (51). Another mechanism by which the VR program can reduce pain would be the creation of a relaxing atmosphere. Perception of pain is influenced by the patient's affect (52). Therefore, the positive effect induced by the psychological effects of the VR relaxation program could suppress pain perception (53).

This research should provide knowledge about the possibility of implementing VR programs in clinical environment, identifying new intervention opportunities in this group of patients.

Technical problems like device failures and technological difficulties may arise in connection with the use of VR technology. However, staff members are available to provide technical support. As possible adverse events we consider

the lack of improvement and positive evolution of the patient. We also consider as an adverse event the performance of exercise with excessive workload. Patients will be informed of the importance of warning the health professional of any incident or setback in their recovery and their right to withdraw from participation in the research at any time.

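### The protocol recruits exactly the number in its power statement (66, or 33 per arm) and states no allowance for missing week-4 outcomes; on a two-sided test, power is about 76% with none missing and falls with each loss

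*Protocol*

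**What the plan says.** The Recruitment section of the protocol gives two figures. The recruitment target reads "a sample size of (n= 66) patients will be recruited". The power statement reads "a sample size of 33 women per cohort could detect a difference in outcomes of 1.0" between the arms, "given a SD of 1.5 and a power of 0.80". The outcome to which the 1.0 refers is not named. Neither the sidedness of the test nor an alpha appears there. The Statistical analysis section sets significance at p < 0.05, again without sidedness, and says that analysis follows intention to treat.

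On outcome collection, Data collection, monitoring, and management provides for "Initial assessment (Pre) and final 4-week assessment (Post"), which the protocol labels T0 and T1. No other outcome visit is planned. The Discussion tells participants of "their right to withdraw from participation in the research at any time", and the Informed Consent Statement repeats that consent may be revoked. Table 1 admits women from gestational week 12 to week 36. No section states an expected loss, an inflation factor or a replacement rule.

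**The concern.** A sample-size formula for two means counts women who contribute an outcome to the comparison. The protocol gives the same number, 33 per arm, as the number to enrol. Any woman without a T1 score then leaves fewer than 33 in her arm. Because T1 is the only post-baseline assessment, she has no intermediate score to draw on, and an intention-to-treat label does not recreate the missing measurement.

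Some missing T1 scores are foreseeable from the protocol itself. Withdrawal is open at any time, the programme asks for 3 × 4 = 12 attended sessions, and a woman who enters at week 36 reaches T1 at about week 40, so some may deliver first.

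At stake is how a null result is read. If the report cites power 0.80 while the analysed trial has noticeably less, a non-significant difference may be taken as evidence that VR adds nothing.

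**Working it through.** **Inputs.** Difference δ = 1.0, SD σ = 1.5 and power 0.80 (Recruitment); alpha 0.05 (Statistical analysis). Two-sided testing is an assumption. The standardised difference is 1.0/1.5 = 0.667. Loss rates and T0–T1 correlations are also assumptions, because the protocol gives neither.

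**Step 1: try to reproduce 33 per arm.** n per arm = 2σ²(z₁₋α/₂ + z₀.₈₀)²/δ².
- Two-sided 0.05: 2 × 2.25 × (1.960 + 0.842)² = 35.3, so 36 per arm (37 by the exact t-test).
- One-sided 0.05: 2 × 2.25 × (1.645 + 0.842)² = 27.8, so 28 per arm (29 by the exact t-test).

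Neither gives 33. Two unstated routes do: one-sided 28/(1 − 0.15) = 32.9, rounded up to 33; or a two-sided baseline-adjusted comparison with a correlation of about 0.3.

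**Step 2: power and detectable difference at the number analysed.** Noncentral t with noncentrality δ/(σ√(2/n)) and 2n − 2 degrees of freedom, two-sided 0.05. At n = 33 the noncentrality is 1.0/(1.5 × √(2/33)) = 2.71. The last column is the difference detectable with 80% power.

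| Analysed per arm | Loss from 33 | Power for 1.0 | Detectable difference |
|---|---|---|---|
| 33 | 0% | 76.0% | 1.05 |
| 30 | 3/33 = 9% | 71.9% | 1.10 |
| 28 | 5/33 = 15% | 68.8% | 1.14 |
| 26 | 7/33 = 21% | 65.4% | 1.19 |

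The normal approximation gives 77.3% at 33 per arm, so the shortfall from 80% does not depend on the t correction. Losing a single woman (65 analysed) gives 75.4%.

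**Step 3: separate the two sources.** Of the gap below 80%, 80 − 76 = 4 points exist with no loss and come from the 33 itself. Loss adds 76.0 − 71.9 = 4.1 points at 30 per arm, 7.2 at 28 and 10.6 at 26.

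**Step 4: what could hold 80%.**
- One-sided 0.05 test: 85.0% at 33 per arm by t-test. Power stays at or above 80% down to 29 per arm (28 by the normal approximation).
- Two-sided comparison of T1 adjusted for T0: residual SD = 1.5√(1 − r²), one further degree of freedom used.

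| Analysed per arm | r = 0.3 (SD 1.43) | r = 0.5 (SD 1.30) |
|---|---|---|
| 33 | 79.8% | 86.8% |
| 30 | 75.8% | 83.4% |
| 28 | 72.8% | 80.7% |
| 26 | 69.5% | 77.7% |

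The adjustment always helps, but whether it restores 80% depends on a correlation that the protocol does not give.

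**The case against.** The strongest objection is that the origin of 33 is undocumented. A reader might infer from 2 × 33 = 66 that the plan assumes nobody is lost. The protocol does not support that reading: 33 is not what its inputs give on a two-sided test, and a one-sided 28 inflated by 15% would give exactly 33. Nothing shows that this route was taken, but nothing excludes it. What can be said is that no allowance is stated.

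A reader might also infer that losses are what push the trial below its stated power. That fails too. On the two-sided reading, power is about 76% with complete data, so losses deepen a shortfall that already exists.

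Other objections have some weight. The right to withdraw is a consent right, not a forecast of attrition, and a woman who stops sessions could still be assessed at T1. The entry limit of week 36 is the better evidence, and even that shows only that losses are plausible. A loss of a few women costs little power. The Results section calls the study a pilot, which softens the risk of over-reading a null result. However, the Objectives set an effectiveness aim and the Recruitment section makes a formal power claim.

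That missing-data methods may sit in a separate analysis plan does not answer the point. The recruitment number and its stated power are fixed in the protocol.

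**Conclusion.** The point holds in this form: the recruited number equals the number in the power statement, no allowance for missing T1 outcomes is stated, and the stated power of 0.80 is not what the design delivers on a two-sided 0.05 test. Power is about 76% if every woman is analysed, and about 72%, 69% and 65% at 30, 28 and 26 analysed per arm. The difference detectable with 80% power rises from 1.05 to 1.10, 1.14 and 1.19.

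These figures rest on the protocol's difference and SD, on assumed two-sided testing, and on assumed losses spread equally over the arms. Only an unstated one-sided test or a sufficiently strong baseline adjustment would hold 80%, and with enough loss neither would. This is a moderate weakness in a stated figure. It does not invalidate the comparison.

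**What to change.** Keep 66 recruited; enrolment began in September 2022 according to the Results section. In the Recruitment section:

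1. State whether the test is one-sided or two-sided.
2. Distinguish women recruited from women analysed, and state the expected share with a T1 outcome.
3. Give the power, or the difference detectable with 80% power, at that analysed number. On the two-sided unadjusted test this would be, for example, 1.10 at 30 per arm or 1.14 at 28.

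In the Statistical analysis section, make the between-arm comparison of T1 adjusted for T0 the main analysis. The T0 scores are already collected. If the stated power relies on this adjustment, report it over a range of assumed correlations (at 28 per arm, 73% at r = 0.3 and 81% at r = 0.5), not at one favourable value.

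The cost is a rewording, with no extra women or visits. The downside is a slightly less favourable stated figure. The change describes the trial's sensitivity correctly. It does not by itself guarantee 80% power, because the correlation is unknown.

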## Objectives

The main objective of this research is to evaluate the effectiveness of a combined VR and Physiotherapy 4-weeks program compared to a standard physiotherapy intervention in LBP and PP pregnancy woman's to improve pain-related fear avoidance, pain intensity, disability and functional level.

The secondary aim is to investigate patient satisfaction with the VR intervention.

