## Results:

Enrollment began in September 2022. First study results will be reported at the end of 2022. The results of this study will determine if a larger-scale intervention is feasible. Further, this pilot study will be the first to examine the effect of the VR intervention on LBP and PP in pregnancy woman. If the results confirm beneficial

effects in the outcomes, this study will add more evidence in support of the use of VR program as an effective tool in pregnancy with LBP and PP rehabilitation programs.

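### The stated power of 0.80 does not follow from 33 women per arm, a difference of 1.0 and an SD of 1.5: at two-sided 0.05 these inputs give about 76%

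*Protocol*

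**What the plan says.** The sample size paragraph is in the protocol under Methods, Recruitment. It says that "a sample size of (n= 66) patients will be recruited" and that "33 women per cohort could detect a difference in outcomes of 1.0 between the VR intervention and control groups". The remaining inputs to this claim stand in the same sentence: "given a SD of 1.5 and a power of 0.80". The total of 66 is exactly 2 × 33. The paragraph gives no significance level, sidedness, test, allowance for loss or covariate adjustment, and it does not say which outcome the difference of 1.0 refers to.

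The significance level comes from the Statistical analysis section: "Statistical significance was set at" p < 0.05, again without sidedness.

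The Objectives section compares the two programmes on several targets, "to improve pain-related fear avoidance, pain intensity, disability and functional level". The Results section adds that "this pilot study will be the first to examine the effect of the VR intervention".

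**The concern.** The protocol presents 0.80 as a calculated result tied to 33 women per arm. Apart from sidedness, the ingredients of a two-sample power calculation are all printed, so the figure can be checked. It does not come out under either reading of sidedness.

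The stated power implies a type II error of 20%. On the two-sided reading it is 23% to 24% even if every woman completes the 4-week assessment, and it rises with each missing assessment, because recruiting exactly 2 × 33 leaves no margin. A null result would then be read against a sensitivity that the design does not have. Because the paragraph speaks only of outcomes in general and the objectives name four targets, a reader also cannot tell which measure the power figure describes.

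**Working it through.** **Inputs**

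- n = 33 per arm, difference Δ = 1.0, SD σ = 1.5, stated power 0.80 (Recruitment).
- α = 0.05 (Statistical analysis). Sidedness is not stated, so both readings are tried.
- Standardised difference: 1.0/1.5 = 0.667.

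**Attempt to reproduce 0.80 at 33 per arm, two-sided 0.05**

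- Standard error of the difference: 1.5 × √(2/33) = 0.369.
- Signal-to-noise ratio: 1.0/0.369 = 2.708.
- Normal approximation: Φ(2.708 − 1.960) = Φ(0.748) = 0.773.
- Noncentral t with 64 degrees of freedom: 0.760.

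The stated 0.80 is not reproduced. The gap is 2.7 points (normal) or 4.0 points (t).

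**Sample size for 80%, two-sided 0.05**

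- Normal: n = 2(1.960 + 0.842)² × 1.5²/1.0² = 35.3, so 36 per arm.
- Noncentral t: 36.3, so 37 per arm.
- Against 33, that is 3 to 4 more per arm, or 6 to 8 in total.

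**One-sided 0.05**

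- Power at 33 per arm: Φ(2.708 − 1.645) = 0.856 (normal); 0.850 (t).
- n for 80%: 2(1.645 + 0.842)² × 1.5² = 27.8, so 28 (normal); 28.5, so 29 (t).

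This reading overshoots 0.80 at 33 and falls short of 33 at 0.80.

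**What would have to be true for 33 per arm to give exactly 0.80**

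| Quantity changed (all else as printed) | t-test | Normal |
|---|---|---|
| Two-sided α | 0.067 | 0.062 |
| One-sided α | 0.034 | 0.031 |
| Difference (two-sided 0.05) | 1.05 | 1.03 |
| SD (two-sided 0.05) | 1.43 | 1.45 |

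**Other routes to 33, each needing an unstated input**

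- One-sided 0.05 plus a loss allowance: 29/0.90 = 32.2, so 33 (t); or 28/0.85 = 32.9, so 33 (normal).
- Baseline-adjusted ANCOVA, two-sided 0.05, with residual SD 1.5 × √(1 − r²) and 2n − 3 degrees of freedom: 80% needs r = 0.31 at 33 per arm, and r = 0.42 if 30 per arm complete.

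**Effect of loss (assumed, since the protocol gives no rate), two-sided 0.05, t-test**

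- About 10% loss, 30 per arm: power 0.719.
- About 20% loss, 26 per arm: power 0.655.

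**The case against.** The strongest counter-argument is rounding. The difference and the SD are printed to one decimal. A true difference of 1.03 with an SD of 1.47 would print as 1.0 and 1.5 and gives t-test power of 0.80 at 33 per arm, two-sided 0.05, with no loss allowance or covariate. This is possible, but nothing in the protocol indicates it. The same rounding intervals (0.95 to 1.05 and 1.45 to 1.55) allow t-test power anywhere from about 0.69 to 0.83, so rounding could as easily put the true figure below 76%. It explains how the mismatch might have arisen without making the sentence correct as printed.

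Second, sidedness is unstated and the alternative hypothesis in the Abstract is directional. Under a one-sided 0.05 test, 33 per arm gives 85%, and the trial would not be underpowered. That stands as a reason not to insist that 76% is the only possible answer. It still does not yield 0.80 at 33. If 33 came from 29 plus a loss allowance, then 0.80 belongs to about 29 evaluable women, whereas the sentence attaches it to all 33.

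Third, the meaning of the SD is not given. If the analysis adjusts for the T0 value, a modest pre-post correlation restores 0.80. Such a correlation is quite plausible, but the protocol neither states one nor names an adjusted analysis in the sample size paragraph.

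Fourth, the trial is called a pilot and a gap of a few points would change no decision. This is a fair limit on how much weight the point carries, and it is why the sample size is left alone. The protocol nevertheless makes evaluating effectiveness its main objective and supports its sample with a formal power claim, so the claim should be right. Nor is this detail that can be left to a statistical analysis plan: the figure is already stated in the protocol, and it does not match the inputs beside it.

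**Conclusion.** The concern holds. Taken as printed and with two-sided 0.05, the inputs give 76.0% (t) or 77.3% (normal) instead of 80%, a shortfall of 2.7 to 4.0 points or 3 to 4 women per arm. One-sided 0.05 does not reproduce the stated pairing either. The 76% rests on three assumptions: a two-sided test, an unadjusted comparison of two means with equal arms, and complete data. The conclusion that 0.80 does not follow from the printed inputs holds under either sidedness. This is a modest error in a stated figure. It should be corrected, but it gives no reason to change the sample size.

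**What to change.** Keep n = 66 and rewrite the power sentence in the Recruitment section, for example:

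> With 33 women per arm, the trial has about 76% power (t-test, two-sided alpha 0.05) for a between-group difference of 1.0 with SD 1.5 on [the primary outcome that the investigators powered on]; 80% power corresponds to a difference of about 1.05. Power is lower with any loss to the 4-week assessment.

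If the investigators wish to keep 0.80, the sentence should give the route that produces it:

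- for a T0-adjusted ANCOVA, the assumed pre-post correlation (at least about 0.31 with complete data, or about 0.42 with 30 completers per arm);
- for a one-sided test with a loss allowance, the sidedness, the assumed loss and the number of evaluable women per arm to which 0.80 applies;
- for rounded inputs, the unrounded difference and SD.

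The cost is one sentence. On the first option the stated power becomes slightly less favourable. No extra patients, procedures or analyses are needed.

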### Intervention

Participants will be assigned randomly to the intervention or control groups using a random number table. Both groups will receive 3 sessions per week during the 4 weeks of intervention.

## Control Group (CG)

Following clinical practice guidelines, subjects in the control group will receive multidisciplinary rehabilitation programmes with coordinated delivery of supervised exercise therapy, cognitive behavioural therapy (education on pain), as well as therapeutic massage to relieve low back pain during pregnancy.

Typical physiotherapy session:

- Control of daily health
- Analgesic and muscle-relaxing (thermotherapy, tens, therapeutic massage)
- Exercise session:
  - o Initial warm-up: 5–10 min (thoracic, lumbar and pelvic joint mobility exercises adapted to the pregnancy progress).
  - o Strengthening and flexibility exercises (thoracic, lumbar and pelvic joint exercises adapted to the pregnancy progress).
  - o Return to calm: 5 min breath and stretching exercises
  - o Recording of incidents and patient/physiotherapist feedback

Experimental Group (EG). VR intervention:

- o Subjects in the experimental group will receive the same treatment described for the control group
- o Subjects in the experimental group will receive an additional VR intervention.

The immersive virtual reality (VRi) system is composed by a head mounted display (Oculus Quest, Facebook Inc.) and two controllers. Oculus Quest headset is a wireless and portable Android-based device which supports positional tracking with six degrees of freedom (360°). The internal cameras allow to show an external signal with the user view, which helps to monitoring the patient execution. A Wi-Fi connection and a training area of 2x2 meters are needed.

At the end of each session, participants will experience an immersive virtual landscape displayed by Nature Trek VR software (<https://naturetreksvr.com/>). First, participants will be placed in a sit down position and guided for their breathing control during 5 minutes (“meditation Lotus option”). After that, they will be encouraged to freely move around a relaxing virtual environment during 15 minutes taking special attention to soothing sounds of nature. The themed environment will be selected based on the preferences of the participants.

At the beginning of the study, advice is given on general care, in physical activity and issues concerning drug intake. Patients are advised to refrain from any other specific training during the intervention period. Any deviations from the adherence and practice of the VRi are recorded daily, noting any adverse incidents.

